6.3.2 Administration of Ipilimumab

Each patient in Arm B is to receive ipilimumab at 1 mg/kg dose IV every 6 weeks of treatment for up to 4 doses after surgery. Ipilimumab will be administered as a 90 +/- 15-minute IV infusion, using a volumetric pump with a 0.2 to 1.2 micron in-line filter at the protocol-specified dose. The drug can be diluted with 0.9% normal saline or 5% Dextrose Injection to concentrations between 1 mg/mL and 4 mg/mL. It is not to be administered as an IV push or bolus injection. Care must be taken to assure sterility of the prepared solutions, since the drug product does not contain any antimicrobial preservatives or bacteriostatic agents.

Please refer to the ipilimumab Investigator Brochure for further details regarding preparation/administration.

6.3.3 Patient monitoring during Ipilimumab infusion

Patient vital signs should be monitored prior to dosing, about 15 minutes after initiation of the infusion (then every 15-20 minutes as indicated), at 30 and 60 minutes after completion of the infusion, or longer if indicated, until the vital signs normalize or return to baseline. For subsequent infusions, vital signs should be collected prior to dosing, every 30 minutes during dosing, and 1-hour post dosing. All vital sign time points will be afforded a 10-minute window.

6.3.4 Treatment of Ipilimumab infusion Reactions

Since ipilimumab contains only human protein sequences, it is less likely that any allergic reaction will be seen in patients. However, it is possible that infusion of ipilimumab will induce a cytokine release syndrome that could be evidenced by fever, chills, rigors, rash, pruritus, hypo- or hypertension, bronchospasm or other symptoms. No prophylactic pre-medication will be given unless indicated by previous experience in an individual patient.

Reactions should be treated based upon the following recommendations:

For mild symptoms (e.g., localized cutaneous reactions such as mild pruritus, flushing, rash):

- Decrease the rate of infusion until recovery from symptoms, remain at bedside and monitor patient;
- Complete the ipilimumab infusion at the initial planned rate;
- Diphenhydramine 50 mg IV will be given prior to subsequent doses for patient who experience infusion reactions of \geq grade 1.
- Premedication with diphenhydramine may otherwise be given at the discretion of the Investigator for subsequent doses of ipilimumab.

For moderate symptoms (any symptom not listed above [mild symptoms] or below [severe symptoms] such as generalized pruritus, flushing, rash, dyspnea, hypotension with systolic BP >80 mmHg):

- Interrupt ipilimumab;
- Administer diphenhydramine 50 mg IV;
- Monitor patient closely until resolution of symptoms;
- Corticosteroids may abrogate any beneficial immunologic effect, but may be administered at the discretion of the treating physician;
- Resume ipilimumab infusion after recovery of symptoms;
- At the discretion of the treating physician, ipilimumab infusion may be resumed at *one half the initial infusion rate, then increased incrementally to the initial infusion rate.*

- If symptoms develop after resumption of the infusion, the infusion should be discontinued and no additional ipilimumab should be administered that day;
- The next dose of ipilimumab will be administered at its next scheduled time and may be given with pre-medication (diphenhydramine and acetaminophen) and careful monitoring, following the same treatment guidelines outlined above;
- At the discretion of the treating physician additional oral or IV antihistamine may be administered prior to dosing with ipilimumab.

For severe symptoms (e.g., any reaction such as bronchospasm, generalized urticaria, systolic blood pressure <80 mm Hg, or angioedema):

- Immediately discontinue infusion of ipilimumab, and disconnect infusion tubing from the subject;
- Consider bronchodilators, epinephrine 1 mg IV or subcutaneously, and/or diphenhydramine 50 mg IV, with Solu-Medrol 100 mg IV, as needed.
- Patients should be monitored until the Investigator is comfortable that the symptoms will not recur;
- No further ipilimumab will be administered;

In case of late-occurring hypersensitivity symptoms (e.g., appearance within one week after treatment of a localized or generalized pruritus), symptomatic treatment may be given (e.g., oral antihistamine, or corticosteroids).

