6.1.5 Treatment of nivolumab Related Infusion Reactions

Since nivolumab contains only human immunoglobulin protein sequences, it is unlikely to be immunogenic and induce infusion or hypersensitivity reactions. However, if such a reaction were to occur, it might manifest with fever, chills, rigors, headache, rash, pruritus, arthralgias, hypo- or hypertension, bronchospasm, or other symptoms. All Grade 3 or 4 infusion reactions should be reported within 24 hours to the BMS and reported as an SAE if criteria are met. Infusion reactions should be graded according to NCI CTCAE (version 4.0) guidelines.

Treatment recommendations for nivolumab related infusion reactions are provided below and may be modified based on MD Anderson treatment standards and guidelines, as appropriate:

- **For Grade 1 symptoms** (Mild reaction; infusion interruption not indicated; intervention not indicated):
 - Remain at bedside and monitor subject until recovery from symptoms. The following prophylactic pre-medications are recommended for future infusions: diphenhydramine 50 mg (or equivalent) and/or acetaminophen 325 to 1000 mg at least 30 minutes before additional nivolumab administrations.
- **For Grade 2 symptoms** (Moderate reaction requires therapy or infusion interruption but responds promptly to symptomatic treatment [e.g. antihistamines, non-steroidal anti-inflammatory drugs, narcotics, corticosteroids, bronchodilators, IV fluids]; prophylactic medications indicated for ≤ 24 hours):

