 - Stop the nivolumab infusion, begin an IV infusion of normal saline, and treat the subject with diphenhydramine 50 mg IV (or equivalent) and/or acetaminophen 325 to 1000 mg; remain at bedside and monitor subject until resolution of symptoms. Corticosteroid or bronchodilator therapy may also be administered as appropriate. If the infusion is interrupted, then restart the infusion at 50% of the original infusion rate when symptoms resolve; if no further complications ensue after 30 minutes, the rate may be increased to 100% of the original infusion rate. Monitor subject closely. If symptoms recur, then no further nivolumab will be administered at that visit. Administer diphenhydramine 50 mg IV, and remain at bedside and monitor the subject until resolution of symptoms. The amount of study drug infused must be recorded on the case report form (CRF). The following prophylactic premedications are recommended for future infusions: diphenhydramine 50 mg (or equivalent) and/or acetaminophen 325 to 1000 mg should be administered at least 30 minutes before additional nivolumab administrations. If necessary, corticosteroids (recommended dose: up to 25 mg of IV hydrocortisone or equivalent) may be used.
- **For Grade 3 or Grade 4 symptoms** [Severe reaction, Grade 3: prolonged (i.e. not rapidly responsive to symptomatic medication and/or brief interruption of infusion); recurrence of symptoms following initial improvement; hospitalization indicated for other clinical sequelae (e.g. renal impairment, pulmonary infiltrates), Grade 4: life-threatening; pressor or ventilatory support indicated]:
 - Immediately discontinue infusion of nivolumab. Begin an IV infusion of normal saline, and treat the subject as follows: Recommend bronchodilators, epinephrine 0.2 to 1 mg of a 1:1,000 solution for subcutaneous administration or 0.1 to 0.25 mg

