of a 1:10,000 solution injected slowly for IV administration, and/or diphenhydramine 50 mg IV with methylprednisolone 100 mg IV (or equivalent), as needed. Subject should be monitored until the investigator is comfortable that the symptoms will not recur. Nivolumab will be permanently discontinued. Institutional guidelines will be followed for the treatment of anaphylaxis. Remain at bedside and monitor subject until recovery from symptoms. In the case of late-occurring hypersensitivity symptoms (e.g. appearance of a localized or generalized pruritus within 1 week after treatment), symptomatic treatment may be given (e.g. oral antihistamine or corticosteroids).

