• HBV viral load ^m	X				X		X ^q		X			
• Anti-HBc (total), anti-HBs, and HBe Ag	X											
CENTRAL Laboratory Assessments												
Blood for genetic analysis		X										
Whole blood for biomarker studies (serum and plasma) ^h		X	X	X	X		X ^q		X			
Whole blood for correlative studies (RNA and DNA) ^h		X	X	X	X		X ^q		X			
Tumor tissue collection ^j	X				X							
Efficacy Measurements												
Tumor imaging ^k	X ^{i,n}				X		X ^q		X			

AFP = alpha fetoprotein; aPTT = activated partial thromboplastin time; Anti-HBc (total) = Total hepatitis B core antibody; Anti-HDV = hepatitis D virus antibody (previously known as 'delta'); anti-HBs = hepatitis B surface antibody; BP = blood pressure; CBC = complete blood count; Discon = discontinuation; ECOG = Eastern Cooperative Oncology Group; FT4 = free thyroxine; HBeAb or anti-HBe = hepatitis B e antibody; HBeAg = hepatitis B e antigen; HBV = hepatitis B virus; HBcAg = hepatitis B core antigen; HBsAb = hepatitis B surface antibody; HBsAg = hepatitis B surface antigen; HCV = hepatitis C virus; HCV Ab = hepatitis C antibody; INR = international normalized ratio; P = pulse; Q12W = every 12 weeks; RR = respiratory rate; T = temperature; PT = prothrombin time; T3 = triiodothyronine; TSH = thyroid-stimulating hormone, ACTH = adrenocorticotrophic hormone .

- a. In subjects that experience site-assessed PD or start a new anti-cancer therapy, contact should be made (example; by telephone) q12W to assess for survival status.
- b. Cycle 1 treatment must be given within 3 days of allocation. The window for each visit is ±3 days until the end of treatment and ±7 days during follow-up. Nivolumab is given every 4 weeks after surgery.
- c. Height will be measured at Visit 1 only. Timepoints of directed physical examination will follow nivolumab and ipilimumab administration day.
- d. For women of reproductive potential, a urine or serum pregnancy test should be performed within 24 hours prior to C1D1, C5D1 and 30 days post treatment. May use screening pregnancy test if performed within 24 hours of first dose. A serum test can be done if urine is not appropriate. Additionally, if urine test is positive or is not evaluable, a serum test is required. Subjects must be excluded/discontinued in the event of a positive test results. Pregnancy tests (serum and/or urine tests) should be repeated if required by local guidelines.

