- r. Ipilimumab 1 mg/kg IV is administered in the adjuvant setting, starting with Cycle 5, every 6 weeks to 4 doses maximum.

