10.3.1.5 Adverse Event Monitoring

An adverse event is the appearance or worsening of any undesirable sign, symptom, or medical condition occurring after starting the study drug even if the event is not considered to be related to study drug. Medical conditions/diseases present before starting study drug are only considered adverse events if they worsen after starting study drug. Abnormal laboratory values or test results constitute adverse events only if they induce clinical signs or symptoms, are considered clinically significant, or require therapy.

Adverse events will be evaluated according to the NCI CTCAE Version 4.0 on a continuous basis starting from when the patient takes the first dose of nivolumab or ipilimumab to follow up visits. Events, such as abnormal laboratory values, considered by the principal investigator to be not clinically significant (related to the study or study drug) will not be documented. **The investigator (or physician designee) is responsible for verifying and**

providing source documentation for all adverse events and assigning the attribution for all adverse events for subjects enrolled. If abnormal lab values, which were not pre-existing or which worsened after the first dose of study drug, meet Common Terminology Criteria (CTC) for reporting as adverse events (AE), they will be documented in the AE source document and captured in the CORE/PDMS Database. For the lab results that do not meet the CTC for reporting as an AE, they will be considered not clinically significant (NCS). No additional documentation will be required to neither specify NCS lab results nor require physician investigator signature.

Adverse events will be treated appropriately. Such treatment may involve changes in nivolumab or ipilimumab therapy including possible interruption or discontinuation, starting or stopping concomitant treatments, changes in the frequency or nature of assessments, hospitalization, or any other medically required intervention. Refer to Sections 6.1-3 for treatments of nivolumab or ipilimumab infusion reaction and toxicities.

Once an adverse event is detected, it should be followed until its resolution, and assessment should be made at each visit of any changes in severity, the suspected relationship to nivolumab or ipilimumab, the interventions required to treat it, and the outcome. Reporting of adverse events will be done according to NCI CTCAE version 4.0. The following items will be recorded at least:

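### For a severe ipilimumab reaction, section 6.3.4 suggests epinephrine 1 mg IV, 4 to 10 times the IV dose in section 6.1.5, with no concentration, rate or deferral to institutional guidelines

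*Combined protocol and SAP*

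**What the plan says.** Section 6.3.4 grades ipilimumab reactions by symptoms. Its severe tier gives bronchospasm, generalized urticaria, angioedema and systolic pressure under 80 mm Hg as examples. The drug advice for that tier is: "Consider bronchodilators, epinephrine 1 mg IV or subcutaneously, and/or diphenhydramine 50 mg IV, with Solu-Medrol 100 mg IV, as needed".

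Section 6.1.5 grades nivolumab reactions by CTCAE grade. For Grade 3 or 4 it recommends "epinephrine 0.2 to 1 mg of a 1:1,000 solution for subcutaneous administration or 0.1 to 0.25 mg". The sentence goes on to specify the preparation and rate for the second of these doses: "of a 1:10,000 solution injected slowly for IV administration". Two further statements there are relevant. The recommendations as a whole "may be modified based on MD Anderson treatment standards and guidelines, as appropriate", and, within the Grade 3 or 4 advice, "Institutional guidelines will be followed for the treatment of anaphylaxis". Section 6.3.4 contains neither statement.

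Elsewhere, section 10.3.1.5 says only: "Refer to Sections 6.1-3 for treatments of nivolumab or ipilimumab infusion reaction and toxicities". The algorithms in Appendix I cover gastrointestinal, renal, pulmonary, hepatic, endocrine, skin and neurological events, not infusion reactions.

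**The concern.** The protocol holds two different IV epinephrine doses for overlapping emergencies. Both sections name bronchospasm, hypo- or hypertension, rash and pruritus among the possible signs, and Arm B patients receive both drugs. The rest of the regimen agrees: each section has diphenhydramine 50 mg IV and methylprednisolone 100 mg IV (named as Solu-Medrol in 6.3.4). The IV epinephrine dose stands out.

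The looser text governs ipilimumab infusions. Section 5.3 has ipilimumab given before nivolumab in Arm B, so a reaction during the ipilimumab infusion is read against 6.3.4. The person at stake is an Arm B patient who has a severe reaction and is given IV epinephrine. The documents give no incidence for this, so the number of such patients cannot be stated.

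**Working it through.** The check is a comparison of texts with simple ratios. No sample size, power or error rate is involved, and the plan states no figure of its own to reproduce.

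**Inputs**

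| Item | 6.3.4 (ipilimumab, severe) | 6.1.5 (nivolumab, Grade 3 or 4) |
|---|---|---|
| IV epinephrine | 1 mg | 0.1 to 0.25 mg |
| IV concentration | not stated | 1:10,000 |
| IV rate | not stated | slow injection |
| Subcutaneous epinephrine | 1 mg, concentration not stated | 0.2 to 1 mg of 1:1,000 |
| Institutional guidelines for anaphylaxis | absent | present |
| May be adapted to institutional standards | absent | present |

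**Dose ratio, 6.3.4 over 6.1.5**

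- IV, against the top of the range: 1 / 0.25 = 4.
- IV, against the bottom of the range: 1 / 0.1 = 10.
- Subcutaneous: 1 / 1 = 1 and 1 / 0.2 = 5. The 1 mg dose is the top of the 6.1.5 range and not above it, so this route does not conflict.

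**Volume.** A 1:10,000 solution is 0.1 mg/mL and a 1:1,000 solution is 1 mg/mL.

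- IV dose in 6.1.5: 0.1 / 0.1 = 1 mL to 0.25 / 0.1 = 2.5 mL of 1:10,000.
- 1 mg in 6.3.4: 1 / 0.1 = 10 mL of 1:10,000, or 1 / 1 = 1 mL of 1:1,000. The section does not say which.

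**Occasions on which 6.3.4 applies.** An Arm B patient has one preoperative ipilimumab dose and up to four adjuvant doses, so up to 1 + 4 = 5 infusions. With 15 patients planned in the arm, the ceiling is 15 × 5 = 75.

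**Adjuvant calendar.** The Arm B footnotes in section 10.0 read "Ipilimumab 1 mg/kg IV is administered in the adjuvant setting, starting with Cycle 5, every 6 weeks to 4 doses maximum" and "Nivolumab is given every 4 weeks after surgery". Counting from Cycle 5 Day 1, ipilimumab falls at weeks 0, 6, 12 and 18, and nivolumab at weeks 0, 4, 8, 12, 16 and 20. They coincide at weeks 0 and 12 only. The ipilimumab doses at weeks 6 and 18 are 14 days from the nearest nivolumab dose, more than the 3 + 3 = 6 days that two visit windows could close. On those two days no nivolumab is planned, so 6.3.4 is the only drug-specific infusion-reaction text in use.

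**Search for a resolving passage.** No other epinephrine instruction appears in the protocol. The cross-reference in 10.3.1.5 leads back to both sections and ranks neither. The Investigator Brochure reference in section 6.3.2 concerns preparation and administration, not treatment of reactions.

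**The case against.** The two sections concern different drugs and grade severity differently. Section 6.3.4 has cytokine release in mind, and nothing says the regimens must match. This is true, but no drug-specific reason for a higher IV dose is offered, and the presentations overlap.

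The text is advisory and offers a subcutaneous alternative that agrees with 6.1.5. A conflict arises only if the clinician chooses epinephrine, chooses the IV route and takes the figure literally. This stands and limits the reach of the point. The protocol nevertheless supplies a number for use in an emergency.

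Staff would probably follow institutional policy whatever the protocol says, and the anaphylaxis sentence in 6.1.5 does not itself name nivolumab. It sits inside the nivolumab Grade 3 or 4 advice, however, and the broader clause on adapting treatment is expressly about nivolumab reactions.

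The strongest objection is timing. Enrollment has stopped, with 27 patients randomized as of January 8, 2020, and the split by arm is not given. The 75 infusions are a planned ceiling, not a count of what remains. With surgery 6 weeks after the first dose, adjuvant start 4 weeks later and the last ipilimumab dose 18 weeks after that, a patient's ipilimumab ends about 6 + 4 + 18 = 28 weeks after the first dose, barring delays. Patients who are not resected go off protocol before any adjuvant dose. An amendment would therefore reach fewer infusions than 75, and the documents do not allow that number to be worked out.

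It is also fair that the calendar adds little: ipilimumab is infused first, so 6.3.4 applies during its infusion on shared days too.

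**Conclusion.** The point holds and should be fixed. Section 6.3.4 suggests an IV epinephrine dose 4 to 10 times that in section 6.1.5. It gives no concentration or rate, and it lacks the institutional-guideline clause that 6.1.5 has. The disagreement is confined to the IV route.

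This rests on the texts alone. It does not assume that 1 mg IV is unsafe or that 0.1 to 0.25 mg is correct; settling that needs clinical sources outside these documents. The number of patients who could be affected is unknown, and closed enrollment makes it smaller than planned, but 6.3.4 remains the current text for any adjuvant ipilimumab still to be given. The safety endpoint, sample size and analyses are not affected.

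**What to change.** Either of two changes to the severe-reaction advice in 6.3.4 would do.

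1. Replace the single 1 mg figure with the route-specific doses of 6.1.5: subcutaneous 0.2 to 1 mg of 1:1,000, or IV 0.1 to 0.25 mg of 1:10,000 by slow injection. The clinical team and pharmacy should confirm these first.
2. Delete the 1 mg IV dose and add the sentence already in 6.1.5: "Institutional guidelines will be followed for the treatment of anaphylaxis". This option needs no judgement about which dose is right and can be justified from the protocol alone.

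The cost is a one-sentence correction in a protocol amendment. No data collection, sample size or trial operation changes.

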7.0 DOSE MODIFICATIONS

Based upon toxicity profiles on past clinical trials (e.g. nivolumab plus ipilimumab in melanoma [43, 44]), the doses of nivolumab and ipilimumab proposed in this protocol are within the maximum tolerated doses. Therefore, dose reductions or modifications of nivolumab and/or ipilimumab will not be allowed.

For detailed management of toxicities related to nivolumab or ipilimumab, please refer to Appendix 1 (AE I-O Algorithms). If a patient experiences a grade 3 or greater drug-related adverse event after a dose of nivolumab or ipilimumab, and did not respond to steroid treatment within 2 weeks (i.e. improve from G4 to \leq G3; or from G3 to \leq G2), then the next dose will not be administered and the patient will proceed to surgery after the adverse event has resolved or been ameliorated sufficiently so that the patient can proceed safely to surgery. If a patient experiences a grade 3 or greater non-drug related adverse event after a dose of nivolumab or ipilimumab then the patient may receive additional doses of nivolumab or ipilimumab, at the discretion of the PI, if the grade 3 or greater event has resolved or has been reduced sufficiently as assessed by the treating PI prior to administration of the additional doses of nivolumab or ipilimumab.

8.0 DISCONTINUATION OF THERAPY

Patients MUST be discontinued from study therapy AND withdrawn from the study for the following reasons:

- Withdrawal of informed consent (subject's decision to withdraw for any reason)
- Any clinical adverse event, laboratory abnormality or inter-current illness which, in the opinion of the Investigator, indicates that continued treatment with study therapy is not in the best interest of the subject
- Termination of the study by MD Anderson Cancer Center
- Imprisonment or the compulsory detention for treatment of either a psychiatric or physical (e.g., infectious disease) illness.

8.1 Discontinuation Criteria of Nivolumab and Ipilimumab

Nivolumab and Ipilimumab administration should be discontinued for the following:

- Any Grade ≥ 2 drug-related uveitis, eye pain, or blurred vision that does not respond to topical therapy and does not improve to Grade 1 severity within the re-treatment period OR requires systemic treatment
- Any Grade 3 non-skin, drug-related adverse event lasting > 7 days, with the following exceptions for laboratory abnormalities, drug-related bronchospasm, hypersensitivity reactions, and infusion reactions:
 - Grade 3 drug-related laboratory abnormalities do not require treatment discontinuation except:
 - Grade 3 drug-related thrombocytopenia > 7 days or associated with bleeding requires discontinuation.
 - Any drug-related liver function test (LFT) abnormality that meets the following criteria require discontinuation:
 - AST or ALT $> 5-10x$ ULN for > 2 weeks
 - AST or ALT $> 10x$ ULN
 - Total bilirubin $> 5x$ ULN
 - Concurrent AST or ALT $> 3x$ ULN and total bilirubin $> 2x$ ULN
 - Grade 3 drug-related bronchospasm, hypersensitivity reaction, or infusion reaction of any duration requires discontinuation

- Any Grade 4 drug-related adverse event or laboratory abnormality, except for the following events which do not require discontinuation:
 - Grade 4 neutropenia ≤ 7 days
 - Grade 4 lymphopenia or leukopenia
 - Isolated Grade 4 electrolyte imbalances/abnormalities that are not associated with clinical sequelae and are corrected with supplementation/appropriate management within 72 hours of their onset.
- Any Grade 4 drug-related adverse event or laboratory abnormality, except for the following events which do not require discontinuation:
 - Grade 4 amylase or lipase abnormalities that are not associated with symptoms or clinical manifestations of pancreatitis. It is recommended to consult with the PI for Grade 4 amylase or lipase abnormalities.
- Any dosing interruption lasting > 6 weeks with the following exceptions:
 - Dosing interruptions to allow for prolonged steroid tapers to manage drug-related adverse events are allowed. Prior to re-initiating treatment in a subject with a dosing interruption lasting > 6 weeks, the principle investigator must be consulted. Tumor assessments should continue as per protocol even if dosing is interrupted.
 - Dosing interruptions > 6 weeks that occur for non-drug-related reasons may be allowed if approved by the principle investigator. Prior to re-initiating treatment in a subject with a dosing interruption lasting > 6 weeks, the UTMDACC IND Office must be notified. Tumor assessments should continue as per protocol even if dosing is interrupted.
- Any adverse event, laboratory abnormality, or inter-current illness which, in the judgment of the Investigator, presents a substantial clinical risk to the subject with continued nivolumab dosing.
- Any Grade 3 drug-related laboratory abnormality, with the following exceptions for asymptomatic amylase or lipase, AST, ALT, or total bilirubin: Grade 3 amylase or lipase abnormalities that are not associated with symptoms or clinical manifestations of pancreatitis do not require a dose delay. It is recommended to consult with the PI for Grade 3 amylase or lipase abnormalities.
- Any Grade 3 colitis, neurologic toxicity, symptomatic pancreatitis, or pneumonitis.
- Any Grade ≥ 3 Stevens-Johnson Syndrome of Toxic Epidermal Necrolysis(TEN).

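### Section 8.1 gives two inconsistent discontinuation rules for grade 3 drug-related laboratory abnormalities

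*Combined protocol and SAP*

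**What the plan says.** Section 8.1 is one list under one lead-in: "Nivolumab and Ipilimumab administration should be discontinued for the following". Two entries deal with grade 3 laboratory results.

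- Rule A is a sub-bullet, nested as an exception under the bullet on grade 3 non-skin events that persist beyond seven days. It reads "Grade 3 drug-related laboratory abnormalities do not require treatment discontinuation except" and then names what does stop drug: "Grade 3 drug-related thrombocytopenia > 7 days or associated with bleeding requires discontinuation", plus four criteria on AST, ALT and bilirubin.
- Rule B is a separate bullet near the end of the list: "Any Grade 3 drug-related laboratory abnormality, with the following exceptions for asymptomatic amylase or lipase, AST, ALT, or total bilirubin". Its explanatory text covers only amylase and lipase without signs of pancreatitis, and says these "do not require a dose delay".

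Grade 4 events are handled by a bullet printed twice with the same stem: "Any Grade 4 drug-related adverse event or laboratory abnormality, except for the following events which do not require discontinuation". The first printing exempts "Grade 4 neutropenia ≤ 7 days", "Grade 4 lymphopenia or leukopenia", and isolated electrolyte disturbances without sequelae that are put right within 72 hours. The second exempts only amylase or lipase elevations without symptoms.

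**The concern.** Two investigators can each follow Section 8.1 and reach different dosing decisions on the same laboratory value. Blood counts and chemistry are drawn on every post-surgical nivolumab day, and in Arm B on ipilimumab days too (Section 10.0, Table 1, footnote f for each arm), so the rule may be consulted at each adjuvant dose. Under Rule B, drug could be stopped for a value that Rule A says does not call for it. This is an operative rule for individual patients, so the text should give one answer.

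**Working it through.** The plan states no figure on this point, so the check sets the bullets side by side.

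**Step 1. Grade 3, drug-related, by type of result.**

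| Grade 3 result | Rule A | Rule B | Agree? |
|---|---|---|---|
| Neutropenia | stop not required | stop | no |
| Lymphopenia or leukopenia | stop not required | stop | no |
| Anemia | stop not required | stop | no |
| Electrolytes | stop not required | stop | no |
| Thrombocytopenia, 7 days or less, no bleeding | stop not required | stop | no |
| Thrombocytopenia, over 7 days or bleeding | stop | stop | yes |
| AST, ALT, bilirubin | stop at listed thresholds | excepted | yes, Rule A governs |
| Amylase or lipase, no symptoms | stop not required | excepted | yes |

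The conflicting rows are examples, not a closed list. Sections 10.3.2.1 and 10.3.2.2 add creatinine, glucose, alkaline phosphatase, uric acid and clotting times, none of which Rule B excepts.

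**Step 2. Does the nesting of Rule A remove the conflict?** Suppose Rule A only carves results out of its parent bullet, leaving Rule B to act independently. Rule B then stops drug for every grade 3 thrombocytopenia, whatever its duration. The duration-or-bleeding qualifier in Rule A would have no effect. Rule A's own sentence is also unqualified.

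**Step 3. Does another section decide?** Section 7.0 bars dose modifications, withholds the next dose after a grade 3 or worse drug-related event that does not respond to steroids, and sends the patient to surgery. It does not address an adjuvant laboratory value. Section 8.0 and a bullet in 8.1 let the investigator stop for clinical reasons, but do not say whether a given value requires it.

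**Step 4. What does Rule B's wording suggest?** It closes on dose delay, inside a list about stopping. It also announces exceptions for AST, ALT and bilirubin but explains only amylase and lipase. Both features fit a fragment of a delay list. The documents do not say that this is its origin.

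**Step 5. Grade 4.** The first printing has 3 exceptions and the second has 1: 3 + 1 = 4 in total, with 0 shared. Read literally, each printing makes the other's exempt events a trigger. The exemptions survive only if the lists are merged.

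**Step 6. Can grade 3 stop drug where grade 4 does not?**

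| Grade 4 lists | Rule B read as | Grade 3 stricter than grade 4? |
|---|---|---|
| literal | stop rule | no, both stop |
| literal | delay rule | no |
| merged | stop rule | yes: neutropenia up to 7 days, lymphopenia or leukopenia, corrected isolated electrolytes |
| merged | delay rule | no |

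The reversal appears in 1 of 4 combinations. Even there it does not reach symptom-free amylase or lipase, which are exempt at both grades.

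**The case against.** The strongest reply is that Section 8.1 is a list of independent triggers. Rule A says only that stopping is not required; it does not instruct anyone to continue. An event spared by one bullet may be caught by another, and a cautious reader would apply the stricter one. On that view the thrombocytopenia qualifier is merely redundant.

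Part of this stands: Rule A is not a positive instruction to keep dosing. But the protocol states no precedence for the stricter bullet, and the reply leaves Rule A's general sentence with little work to do. The ambiguity remains.

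Several stronger readings are tempting and are not supported:

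- A reader might infer that the protocol plainly stops drug for milder events and continues it for worse ones. Step 6 shows that this needs the grade 4 lists read by intent and Rule B read literally.
- A reader might infer permanent loss of adjuvant drug. That is the worst case: Section 8.1 itself mentions re-treatment and restarting after interruption, and Section 10.3.1.5 records temporary as well as permanent discontinuation.
- A reader might infer that the conflicting events are common. The documents give no frequencies for them in this trial. The nivolumab data in HCC (Section 3.3.2) report grade 3 liver-enzyme rises and one grade 4 lipase elevation. At grade 3, liver enzymes and symptom-free lipase are groups on which the two rules do not clash.

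**Conclusion.** The inconsistency is real and is in the current text. Grade 3 drug-related laboratory abnormalities outside the listed exceptions get conflicting instructions under one discontinuation heading. The duplicated grade 4 bullet is a minor companion flaw, since the union of its exceptions is evidently intended.

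Severity is minor. Rule B read literally errs toward stopping drug, and enrollment has stopped (Section 5.3), so the rule matters mainly for remaining adjuvant dosing. The number of patients affected cannot be computed. Counting the doses a full adjuvant course could contain would not size the effect, because it says nothing about how often the conflict arises. No endpoint or statistical figure changes.

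The conflict itself rests only on the wording. That Rule B is a misplaced delay criterion is an inference, and the grade reversal is conditional on the readings in Step 6.

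**What to change.** First have the investigators and the IND Office confirm what Rule B was meant to do. If the intent was a delay:

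- Relabel Rule B as a dose-delay criterion. This is preferable to deleting it, because deletion would remove a safety hold on the strength of an inference.
- State that Rule A, with its platelet and liver-test exceptions, governs discontinuation for grade 3 laboratory results.
- Leave Section 7.0 in force.
- Merge the two grade 4 bullets into one with all four exceptions: neutropenia of at most 7 days; lymphopenia or leukopenia; isolated electrolyte abnormalities without sequelae corrected within 72 hours; and amylase or lipase elevation without symptoms.

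The cost is a wording-only amendment, with no new data or procedures.
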